To evaluate the efficacy of a group-based yoga intervention for urinary incontinence in ambulatory middle-aged and older women and explore potential mediators of intervention effects in this population.

Study Design

Randomized, multicenter, parallel-group trial of a 12-week yoga intervention versus non-specific muscle stretching/strengthening control intervention for ambulatory women aged 45 years and older with urinary incontinence.

Sample Size and Population

Two hundred fifty women aged 45 years and older who document stress-, urgency-, or mixed-type incontinence occurring at least once per day, are not participating in other organized yoga or muscle stretching/strengthening activities, are temporarily willing to forgo other established clinical treatments for incontinence, and meet minimum mobility and other clinical eligibility criteria, recruited from multiple locations in northern California.

Interventions and Duration

Participants will be randomized in a 1:1 ratio to participate in either a 12-week yoga program (N~120) or a time-equivalent non-specific muscle stretching/strengthening control program (N~120). Women randomized to the yoga program will take part in twice weekly group yoga classes focusing on Iyengar/alignment-based yoga techniques and practice yoga at home for at least one hour per week for 12 weeks. Women randomized to the control program will take part in twice weekly group classes focusing on non-specific muscle stretching/strengthening exercises and practice these exercises at least one hour per week at home for 12 weeks.

Study Outcomes

The primary outcome is change in the frequency of any urinary incontinence episodes between baseline and 12 weeks, measured using validated voiding diaries. Secondary outcomes include changes in the frequency of stress-type, urgency-type, daytime, and nighttime incontinence episodes (also measured by voiding diaries), as well as changes in incontinence-related functioning or quality of life (measured by validated questionnaires), between baseline and 12 weeks. Additional secondary outcomes include persistence of changes in incontinence frequency and condition-specific quality of life 12 and 24 weeks after the end of the intervention programs.

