9.2 Sample Size

Sample size has been calculated based on parameter estimates derived from both the investigators' past pilot studies on yoga as well as other group-based incontinence intervention trials conducted by study team members.¹⁰³ Assumptions include: a) average baseline frequency of incontinence of ~23-24 episodes/week; b) standard deviation (SD) of change in incontinence frequency of ~14.4; c) correlation between outcome values of ~0.59; and d) loss of ~15% by 3 months. Assuming a ~50% decrease in incontinence frequency among controls (which is the threshold at which women with daily incontinence start to perceive meaningful benefit from treatment¹⁸), the team will power the study to detect a between-group difference in reduction in incontinence of at least 20% in the yoga versus stretching/strengthening control group (corresponding to a \geq 70% reduction in frequency of incontinence in the yoga group) at 3 months. Under these assumptions, a sample size of 240 (120 per group) will provide 80% power in 2-sided tests with 5% type-I error to detect a between-group difference in reduction in the primary outcome of total incontinence frequency of at least 20% in the yoga vs. control arm. With regard to secondary outcomes, this sample will also provide 80% power to detect moderate between-group differences of 0.26 to 0.39 SDs, assuming intraclass correlation of outcomes in the range of 0.4-0.8.

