9.5 Outcomes

9.5.1 Primary Efficacy Outcome

The primary efficacy outcome will be change in the average frequency of any urinary incontinence over 12 weeks based on a validated 3-day voiding diary. To that end, frequency of incontinence will be assessed based on voiding diaries completed at screening/baseline, 6 weeks, and 12 weeks. If improvement in incontinence is observed over 12 weeks, additional analyses may explore persistence of benefits 12 and 24 weeks after the completion of the yoga or stretching/strengthening programs.

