9.6 Data Analyses

9.6.1 Analyses to address main objectives

Objective 1: To determine the efficacy of a group-based yoga intervention in reducing the frequency of urinary incontinence in ambulatory midlife and older women.

Hypothesis 1A: Ambulatory incontinent women randomized to the yoga intervention will demonstrate at least a 20% greater decrease in total incontinence frequency (measured by validated voiding diaries) over 12 weeks, compared to women randomized to the control intervention.

Hypothesis 1B: If improvements in total incontinence frequency are observed at 12 weeks, these improvements will be sustained 12 and 24 weeks after the end of the intervention programs.

Planned analyses: Intervention effects on the primary outcome of total incontinence frequency will be estimated using a linear mixed model (LMM) for changes since baseline in the overall frequency of any incontinence episodes at 6 and 12 weeks, adjusting for baseline incontinence frequency. Analyses will be by intention to treat, according to intervention group assignment, and without regard to adherence to intervention classes or practice. The LMM will account for clustering using nested random effects for group intervention class series and individual participant. In addition to fixed effects for study location and type of incontinence, the LMM will include terms for intervention, time, and the time-by-intervention interaction, thus allowing for secular trends in controls, as well as different intervention effects at 6 and 12 weeks. The intervention effect will be summarized by an orthogonal contrast capturing any linear trend across 6 and 12 weeks; this makes use of information for participants with 6 but not 12 week outcomes. If the yoga intervention appears effective over 12 weeks, we will also assess maintenance of effects over time, by comparing changes since baseline at 12 weeks with those at 24 and 36 weeks, using an additional LMM. Intervention effects will again be summarized by an orthogonal contrast for linear trend across the three time points.

Objective 2: To determine the efficacy of a group-based yoga intervention in reducing the frequency of type- and context-specific urinary incontinence in ambulatory middle-aged and older women.

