Hypothesis 2A: Ambulatory incontinent women randomized to the yoga intervention will report decreases in the frequency of stress-type, urgency-type, daytime, and nighttime incontinence (also measured by voiding diaries) over 12 weeks, compared to women randomized to the control intervention.

Hypothesis 2B: If improvements in stress-type, urgency-type, daytime, and nighttime incontinence frequency are observed at 12 weeks, these improvements will be sustained 12 and 24 weeks after the end of the intervention programs.

Planned analyses: For additional confirmation of effects on the primary outcome of total incontinence frequency, we will examine effects on frequency of urgency

incontinence episodes and stress incontinence episodes, again using the modeling approach indicated above. Additional models will explore effects on frequency of daytime and nighttime incontinence.

Objective 3: To determine the efficacy of the yoga intervention in improving incontinence-related functioning and quality-of-life.

Hypothesis 3A: Ambulatory incontinent women randomized to the yoga intervention will report greater improvements in condition-specific functioning and quality of life (assessed by validated questionnaires) over 12 weeks, compared to women randomized to the control intervention.

Hypothesis 3B: Compared to women randomized to the control intervention, we hypothesize that women randomized to the yoga intervention will report sustained improvements in condition-specific quality of life 12 and 24 weeks after the end of the intervention programs.

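### The 24- and 36-week incontinence-frequency comparison is a listed secondary outcome, yet it is planned only if an undefined 12-week condition is met

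*Combined protocol and SAP*

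**What the plan says.** The Précis (Study Outcomes) attaches no condition: "Additional secondary outcomes include persistence of changes in incontinence frequency and condition-specific quality of life 12 and 24 weeks after the end" of the programs. Section 3 likewise says that persistence of effects on incontinence frequency will be explored, without a condition.

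The statistical sections differ. Under Objective 1, Section 9.6.1 states: "If the yoga intervention appears effective over 12 weeks, we will also assess maintenance of effects over time". The analysis is a further mixed model of change from baseline at 12, 24 and 36 weeks, summarized by a linear-trend contrast. Section 9.5.1 is looser: "If improvement in incontinence is observed over 12 weeks, additional analyses may explore persistence of benefits 12 and 24 weeks after the completion" of the programs. Hypotheses 1B and 2B are also worded conditionally on improvement at 12 weeks. Section 9.5.2 defines the diary-based secondary outcomes over 12 weeks only.

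Quality of life is treated differently. Hypothesis 3B has no condition ("women randomized to the yoga intervention will report sustained improvements in condition-specific quality of life 12 and 24 weeks after" the programs end), and Section 9.5.2 lists the questionnaires at both post-intervention times.

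Sections 6.2.5 and 6.2.7 schedule a voiding diary at both later times for all participants. Section 8 keeps women who stop the intervention in follow-up through 36 weeks where that is safe, feasible and appropriate.

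**The concern.** The decision to analyse a listed secondary outcome is tied to the primary result. Sections 6.2.4 and 9.3 end blinding for the 12-week period once that dataset is complete, so whoever decides whether the condition is met, or whether to use the option in 9.5.1, will know the 12-week result.

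Three things are at stake. A benefit that emerges after 12 weeks, or a real benefit that the 12-week test misses, would have no planned estimate at 24 or 36 weeks. If later results appear only after a favourable 12-week result, they will on average be too high, because 12- and 36-week estimates from the same women are correlated. And with no stated criterion, two analysts could reach opposite decisions from the same data.

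**Working it through.** **1. The texts side by side (incontinence frequency)**

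| Place | Condition | Commitment |
|---|---|---|
| Précis, Study Outcomes | none | secondary outcome |
| Section 3 | none | will be explored |
| 9.5.1 | an improvement is seen | optional |
| 9.5.2 | not applicable | diary outcomes over 12 weeks only |
| 9.6.1, Objective 1 | yoga looks effective | will be assessed |
| Hypotheses 1B, 2B | improvement at 12 weeks | hypothesis |

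The two conditions are not equivalent. The one in 9.6.1 suggests a between-arm result. The one in 9.5.1 could be met by improvement within arms, and Section 9.2 assumes that controls alone improve by about 50%. On that reading it would nearly always be met. Section 9.6.2 does give a criterion (alpha 0.05) for its conditional dose analysis; none is given here. Section 9.6.2 also allows an exploratory look at home practice and maintenance of effects, but that is not a comparison of the arms.

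**2. Reproducing the sample size**

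Inputs from Section 9.2: "average baseline frequency of incontinence of ~23-24 episodes/week"; "standard deviation (SD) of change in incontinence frequency of ~14.4"; correlation 0.59; 15% loss; a 20-point difference; "80% power in 2-sided tests with 5% type-I error"; 240 women, 120 per arm.

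- Residual SD = 14.4 × √(1 − 0.59²) = 11.63. The plan does not state this adjustment, but of the variants tried only this one comes close to 240; the unadjusted 14.4 gives 336-364.
- Target difference at baseline 23: 0.20 × 23 = 4.6 episodes/week.
- n per arm = 2 × (1.96 + 0.84)² × 11.63² / 4.6², giving 101; 101/0.85 gives 119; total 238, against 240 stated. At baselines 23.5 and 24 the totals are 230 and 220, so the match is at the low end of the range.

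**3. How often the condition fails, if read as p<0.05 favouring yoga**

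Completers per arm = 120 × 0.85 = 102. SE = 11.63 × √(2/102) = 1.63. P(met) = Φ(difference/SE − 1.96).

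| True effect | Difference (baseline 23 to 24) | P(met) | P(not met) |
|---|---|---|---|
| Full target | 4.6 to 4.8 | 0.81 to 0.84 | 16-19% |
| Three quarters | 3.45 to 3.6 | 0.56 to 0.60 | 40-44% |
| Half | 2.3 to 2.4 | 0.29 to 0.31 | 69-71% |

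**4. Selection of high estimates**

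Take baseline 23.5, 90 completers per arm at 36 weeks (120 × 0.75, the upper bound on dropout in Section 9.6.2), a fully maintained effect, and an assumed correlation of 0.4 to 0.8 between the 12- and 36-week estimates. By simulation, the mean 36-week estimate among trials meeting the condition is 3.2 to 4.0 when the true difference is 2.35, and 4.9 to 5.1 when it is 4.7. The distortion is small at the full target effect and large at half of it.

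**5. What unconditional estimation would give**

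With 96 (120 × 0.80) and 90 completers per arm and the same SD, 95% CI half-widths are 1.96 × 11.63 × √(2/96) = 3.3 and 1.96 × 11.63 × √(2/90) = 3.4 episodes/week, against 3.2 at 12 weeks.

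**6. The trend contrast does not supply the differences**

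With weights −1, 0, 1 at 12, 24 and 36 weeks, arm differences of 4.7, 4.7, 4.7 give −4.7 + 4.7 = 0, and differences of 0, 0, 0 also give 0. The contrast cannot tell a fully maintained benefit from no benefit, so the differences themselves need to be reported even when the condition is met.

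**The case against.** Making a maintenance claim conditional on a positive primary result is ordinary hierarchical practice, and persistence can be read as presupposing a 12-week change, as Hypothesis 1B does. That stands for the formal claim. It does not justify making estimation and reporting conditional, or leaving the condition undefined.

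A second objection is that the conflict is one of status: only the Précis gives the secondary-outcome label, while 9.5.1 makes the analysis optional and 9.5.2 confines diary outcomes to 12 weeks. That is fair; it is an inconsistency between sections, and it still needs resolving.

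A third is that the percentages rest on a criterion that the plan does not state and on a simpler test than the planned one, which is a mixed-model contrast across 6 and 12 weeks with random effects for class series. This also stands. The figures size the consequence under one reading; they do not show that the conflict exists.

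A reader might go further in three ways that the documents do not support:

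- That every 24- and 36-week comparison is conditional. Quality of life is not expressly so. A condition could be argued only from the reference back to the Objective 1 modeling strategy.
- That the later data will be discarded or withheld. Nothing says this; the plan is silent on what happens if the condition fails.
- That a control group catching up with yoga would be missed. If a 12-week gap is detected, the condition is met and the 12/24/36-week model examines exactly that. The worry remains only where the gap was missed at 12 weeks or the benefit came late.

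**Conclusion.** The point holds for incontinence frequency. A secondary outcome listed without a condition in the Précis becomes conditional in Sections 9.5.1 and 9.6.1 on two different, undefined readings of a known 12-week result, with no planned between-arm analysis otherwise.

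The size depends on the reading. If any improvement suffices, the condition is almost always met and little is lost. If it means p<0.05 favouring yoga, it fails about 16-19% of the time at the full target effect and 40-44% at three quarters of it, under the Section 9.2 inputs, 102 completers per arm and a baseline-adjusted two-arm comparison at 12 weeks. The primary analysis and the sample size are unaffected. This is an inexpensive improvement, not a fault in the main comparison.

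**What to change.** 1. In Sections 9.5.1 and 9.6.1 (Objectives 1 and 2), state: *The yoga-control difference in change from baseline in incontinence frequency at 24 and 36 weeks will be estimated with 95% CI in all randomized women, whatever the 12-week result, in addition to the linear-trend contrast.*
2. Keep a condition only for the formal claim that a 12-week benefit was maintained (Hypotheses 1B and 2B), and define it once, for example as the primary contrast at p<0.05 favouring yoga.
3. Align the Précis and Sections 9.5.1, 9.5.2 and 9.6.1 on whether these are secondary or exploratory outcomes.
4. Confirm that the Objective 3 analyses at 24 and 36 weeks are not conditional.

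The change is best made before the 12-week unblinding described in Section 9.3. It costs some wording and one model on diaries that are scheduled anyway, with no change in sample size. The downside is a few more secondary estimates, to be labelled as such.

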9.6.2 Other analytic issues

Participant dropout (i.e., early termination or loss-to-follow-up). Participant dropout levels are expected to be <15% at 12 weeks of intervention, <20% at 12 weeks post-intervention follow-up, and <25% at 24 weeks post-intervention follow-up, assuming a similar rate of attrition over time. The assumption of non-informative dropout will be assessed by comparing baseline characteristics and early post-randomization outcomes of dropouts vs. non-dropouts. If dropout rates differ between groups, sensitivity analyses to evaluate the effects of participant dropout on estimates of intervention effects may be run using inverse probability of retention weights, which can legitimately include post-randomization variables associated with dropout. Alternately or in addition to this, we may use multiple imputation of missing outcomes under plausible informative missingness assumptions.¹⁰⁴

Dose effects (length of exposure and intensity of practice). In the event that the primary analysis shows that yoga intervention is effective in reducing incontinence frequency over 12 weeks, we may use a closed test procedure to assess for dose response in length of intervention exposure without inflating type-I error.¹⁰⁵ Specifically, if we detect a statistically significant benefit over 12 weeks an alpha of 0.05, we may assess change from baseline to 6 weeks, and from 6 weeks to 12 weeks, also at alpha of 0.05, based on contrasts that can be obtained from the primary analysis model. In exploratory analyses, we may also examine whether cumulative hours spent in group intervention classes (based on class attendance logs), or total hours of home yoga or stretching/strengthening practice (documented by participants' home practice logs), are associated with changes in incontinence frequency or secondary outcomes in each group. After the end of the 12-week intervention, additional exploratory analyses may examine associations between continued yoga or control intervention practice (based on continued home practice hours) and maintenance of intervention effects.

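### The maintenance model omits the 6-week diary, so the late yoga–control differences are biased if dropout between weeks 6 and 12 follows early response differently in the two arms

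*Combined protocol and SAP*

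**What the plan says.** Section 9.6.1, Objective 1, describes two mixed models. The primary model takes changes at 6 and 12 weeks, adjusts for baseline frequency and has "nested random effects for group intervention class series and individual participant". One stated advantage of its summary contrast is that "this makes use of information for participants with 6 but not 12 week outcomes".

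The second model is conditional: "If the yoga intervention appears effective over 12 weeks, we will also assess maintenance of effects over time". It works by "comparing changes since baseline at 12 weeks with those at 24 and 36 weeks, using an additional LMM", and the text adds: "Intervention effects will again be summarized by an orthogonal contrast for linear trend across the three time points". Week 6 is not among those three points. No separate covariance structure is given for this model, so I read it as carrying over the random effects of the primary one.

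Section 9.6.2 expects dropout of "<15% at 12 weeks of intervention, <20% at 12 weeks post-intervention follow-up, and <25% at 24 weeks post-intervention follow-up". It states: "The assumption of non-informative dropout will be assessed by comparing baseline characteristics and early post-randomization outcomes of dropouts vs. non-dropouts". The remedies follow a condition, "If dropout rates differ between groups, sensitivity analyses to evaluate the effects of participant dropout", and are worded as things that may be done: retention weighting, which is allowed to use post-randomization variables, and multiple imputation under informative missingness. Neither is tied to the maintenance model.

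**The concern.** A likelihood-based mixed model gives valid estimates under missing-at-random dropout only when the observed outcomes that predict dropout are in the model. Section 9.6.2 itself looks to early outcomes to judge whether dropout is informative. The primary model contains the 6-week response. The maintenance model does not, although cumulative loss is larger by then.

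Participants know their assignment and the two programs differ, so reasons for leaving could differ by arm. The Précis lists persistence at 12 and 24 weeks after the programs as an additional secondary outcome. Hypothesis 3B is worded as a comparison with control, so it needs the late between-arm differences and not only the trend. If poor early responders leave yoga but not control, those differences flatter yoga. If the pattern is reversed, they understate it.

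**Working it through.** **Inputs from Section 9.2.** Baseline about 23–24 episodes/week (23.5 used here); SD of change 14.4; correlation r = 0.59; 20-point difference in reduction, so 0.20 × 23.5 = 4.7/week; 120 per arm; 15% loss by 3 months.

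**The plan's own figure.** With baseline-adjusted SD 14.4 × √(1 − 0.59²) = 11.63, baseline 23 (difference 4.6) and 15% loss, 101 per arm are needed after loss. That is 101/0.85 ≈ 119 per arm, or N = 238, close to the stated 240. The sample size is not in dispute. The documents give no figure for the maintenance analysis.

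**Assumptions not in the documents.** Loss between weeks 6 and 12 of 7.5% or 15% (18 or 36 of 240 women). Dropout logistic in the 6-week change, slope 0.7 or 1.5 per SD. Complete data afterwards. No class effect, since no class correlation is given. True difference −4.7 at weeks 12, 24 and 36 (yoga minus control; negative favours yoga), so the true trend is 0.

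**Formula.** Take 14.4 as the SD of a change score and the correlation between any two visits as 0.59. Given baseline, the residual SD at a visit is 14.4 × √((1 + 0.59)/2) = 12.84, and the correlation between two follow-up visits is r/(1 + r) = 0.59/1.59 = 0.371. If dropout moves the mean 6-week residual of retained women in one arm by m SDs, that arm's later means move by 0.371 × 12.84 × m = 4.764 m. The shift m is the mean of z(1 − p(z)) divided by (1 − loss), where z is standard normal and p(z) is the logistic dropout probability with its intercept set to give the stated loss.

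Bias in the late difference (the same at weeks 12, 24 and 36):

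| Loss, slope | m | Poor responders leave yoga only: 4.764 m | Opposite rules by arm: 2 × 4.764 m | Common absolute rule |
|---|---|---|---|---|
| 7.5%, 0.7 | −0.0506 | −0.24 | −0.48 | +0.03 |
| 7.5%, 1.5 | −0.0939 | −0.45 | −0.89 | +0.10 |
| 15%, 0.7 | −0.0986 | −0.47 | −0.94 | +0.06 |
| 15%, 1.5 | −0.1751 | −0.83 | −1.67 | +0.16 |

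The last column takes the 6-week effect as 60% of the 12-week effect. At 100% the largest entry is about +0.3. If the rule is the same relative to each arm's own mean, the shifts cancel and the bias is zero. Simulation with 1,000,000 women per arm gives the same figures to within 0.01. With correlation 0.8 the worst opposite-rule case is −2.1.

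For scale, the standard error of a late difference is 12.84 × √(2/120) = 1.66 with no loss and 12.84 × √(2/90) = 1.91 with 25% loss.

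**The planned trend contrast (week 36 minus week 12).** Under constant correlation the bias is the same at each visit, so the trend bias is 0. It appears only when correlation decays with time. Worst case (15%, slope 1.5, opposite rules):

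- Mild decay (0.59 at 12 weeks, 0.46 at 36): −1.84, −1.63, −1.46 at weeks 12, 24 and 36; trend +0.38.
- Autoregressive decay (0.59 falling to 0.21): −2.74, −1.62, −0.97; trend about +1.8.

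In these cases the trend points toward apparent waning of the effect.

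**Does adding week 6 cure it?** Under constant correlation, yes: bias is within 0.03 in every scenario run, and retention weights based on the 6-week change do equally well. Under decay it depends on the covariance. The next table uses 10% loss, slope 0.7, opposite rules and autoregressive decay. The random-intercept row uses a working variance and covariance averaged over visits.

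| Model | Week 12 | Week 24 | Week 36 | Trend |
|---|---|---|---|---|
| 12/24/36 as planned | −1.04 | −0.62 | −0.36 | +0.68 |
| Four visits, participant random intercept only | −0.50 | −0.07 | +0.18 | +0.68 |
| Four visits, unstructured covariance | 0 | 0 | 0 | 0 |

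A random intercept passes the same correction to every later visit, so it cannot change the trend.

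**Does the Section 9.6.2 trigger fire?** In the yoga-only and opposite-rule scenarios the dropout rates are equal in the two arms by construction. A trigger based on unequal rates would miss them.

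**The case against.** The strongest reply is that the planned summary is a trend contrast, which has no bias under the constant correlation that a participant random intercept implies. That stands as far as it goes. Constant correlation is an assumption, though, and Hypothesis 3B needs the late differences as well as the trend.

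Second, retention weighting on the 6-week diary is within the plan's reach and works. This also stands, but it is optional, tied to unequal rates and not assigned to this model. Because study-wide unblinding follows the 12-week data lock (Sections 6.2.4 and 9.3), a choice left open could be made after unblinding.

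Third, a reader might infer that any dependence of dropout on early response biases the late differences. The calculation does not support that: a rule common to both arms gives at most about 0.3/week, toward no effect. Nothing in the documents says the rules would differ by arm, and the largest figures need opposite rules.

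Fourth, a reader might treat the full 20–25% late loss as exposed. Women lost after week 12 usually have a 12-week diary, which is in the model. A woman who misses week 12 but returns later still contributes, and those who stop classes are followed where possible (Sections 6.2.6 and 8). The gap is mainly loss between weeks 6 and 12, which the documents do not split out from the 15%.

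**Conclusion.** The concern holds in a conditional form. The maintenance model excludes women with a 6-week diary and nothing later, and it does not condition on 6-week response. If loss between weeks 6 and 12 depends on early response differently by arm, the 12-, 24- and 36-week differences are off by roughly 0.2 to 1.7 episodes/week against 4.7. At the top of that range the bias is close to one standard error; in most scenarios it is well below. The range rests on assumed loss, assumed slopes and constant correlation of 0.59. Stronger correlation widens it, and decay widens it at week 12 in particular. Under a common rule the bias is near zero. The trend contrast is affected only if correlation decays.

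A reader might infer that the trial's main result is in doubt. It is not: the 6/12-week primary model already contains the 6-week outcome, and the maintenance analysis is run only after an apparent 12-week effect. This is a worthwhile improvement to a conditional secondary analysis, not a flaw in the trial's main conclusion.

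**What to change.** Fit the maintenance model to all four post-baseline visits (6, 12, 24 and 36 weeks), with categorical time by arm and the same baseline adjustment. Use an unstructured within-participant covariance in place of the participant random intercept alone, and keep the class-series random effect. Take the 12-, 24- and 36-week differences and the maintenance contrast from this one model. Do the same for Hypotheses 2B and 3B, whose diary and questionnaire outcomes are also collected at 6 weeks (Sections 6.1.1 and 6.1.2).

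Leave the 6/12-week primary analysis as it is, and state that it remains the source of the reported 12-week effect. The four-visit model will give its own 12-week estimate, just as the three-visit model would, so that duplication is no argument for or against the change.

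An alternative is to make retention weighting on the 6-week outcome mandatory for this analysis, whatever the dropout rates. Either way the cost is SAP wording. No new data are needed, and the text should be settled before the late data are analyzed.
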